8. SAFETY

All safety analysis reporting will be based on the SAF.

8.1. Adverse Events

Treatment emergent adverse events (TEAEs) are defined as all events that occur from the time of first study drug administration until 30 days following the last dose of study drug or initiation of subsequent cancer-related therapy, whichever occurs first. TEAEs are assessed for severity using the NCI-CTCAE v. 4.0, relationship to each therapy, and seriousness. For Phase 1 data, infusion-related reactions (IRRs) are those which: have an onset date on or one day after the date of a CRS-207 administration; have been identified as related to CRS-207; and are coded to the following specific preferred terms: dyspnoea, chills, decreased appetite, fatigue, headache, hives, hypersensitivity, hypotension, hypoxia, influenza like illness, infusion related reaction, myalgia, nausea, pain, presyncope, pyrexia, rash, and vomiting. Phase 2 IRRs are identified by the investigator using the appropriate eCRF field.

A summary of TEAEs will be produced, including counts and percentages of subjects with any incidences of: TEAEs, CTCAE Grade 3 or higher TEAEs, TEAEs related to any study treatment, CTCAE Grade 3 or higher TEAEs related to any study treatment, serious adverse events (SAEs), SAEs related to any study treatment, TEAEs leading to study drug discontinuation, CRS-207 infusion related reactions, and fatal TEAEs.

Sponsor: Aduro Biotech, Inc.
Protocol Number: ADU-CL-11
Version and Date: Version 1.0, 03MAY2018

A separate summary of AEs identified as CRS-207 IRRs will include the number of infusions received by subjects, the number of subjects having an IRR, total number of IRRs per subject, maximum IRR grade, and dose modifications resulting from IRRs.

Adverse events will be coded based on the Medical Dictionary for Regulatory Affairs (MedDRA) version 18.1 or higher, for reporting by system organ class (SOC) and preferred term (PT) in descending order of overall incidence for the type of event reported. Within these summaries, TEAEs will be sorted for each subject by PT and severity; subjects will be counted once within a PT based on their TEAE having maximum severity.

Summaries of AEs by SOC and PT will include the following types of events:

- TEAEs;
- TEAEs related to any study treatment (Definitely Related, Probably Related, or Possibly Related);
- CTCAE Grade 3 or higher TEAEs;
- CTCAE Grade 3 or higher TEAEs related to any study treatment;
- CRS-207 infusion-related reactions;
- SAEs;
- SAEs related to any study treatment;
- TEAEs that lead to discontinuation of study drug; and
- Fatal TEAEs.

To account for potential differences in the extent of exposure between the treatment categories, a subject-year adjusted rate will also be presented. The rate is calculated as the number of subjects with an event divided by the total subject-years of safety observation, where subject-years of safety observation for each subject is defined as duration of safety observation (defined in Section 5.3) in days divided by 365.25.

A comprehensive listing of all AEs will be provided in a by-subject data listing; events which do not occur during the on therapy period will be identified. In addition, the following listings will be provided:

- SAEs;
- TEAEs leading to treatment discontinuation; and
- Fatal TEAEs (with identification of those which occur within the on therapy period).
- Dose limiting toxicities (DLTs)
- AEs of special interest (AESIs), as defined in Section 9.1.2 of the study protocol

Deaths

The number and percentage of subjects who died along with primary cause of death will be summarized overall (including the post-study survival surveillance period) and within 30 days of last dose of study drug. All death data will be listed.

Sponsor: Aduro Biotech, Inc.
Protocol Number: ADU-CL-11
Version and Date: Version 1.0, 03MAY2018

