5.3. Study Day and Duration Variables

Reference date calculations will be defined as the following:

- date of interest – reference date + 1 when the date of interest \geq reference date;
- otherwise, date of interest – reference date.

For instance, study day will be based on the date of first study treatment as the reference would either have a negative value if collected before dosing or a positive value if collected after drug dosing; there will be no study day zero.

Duration of time is dependent on reference dates and will be calculated in a manner similar to that of the reference date calculation, assuming that dates of interest will strictly follow reference dates (e.g. no negative values). For example, duration on study treatment is defined as the end of study date – first dose date + 1. Duration of treatment is defined as the last date of treatment – first dose date + 1. Duration of the safety observation period is defined as (the last date of treatment + 30 days) – first dose date + 1. Subjects still receiving ongoing treatment or participating in study follow up at the time of analysis will use imputed treatment end and end of study dates as described in Section 5.6.

Survival, or time-to-event, endpoints such as progression-free survival (PFS) or overall survival (OS) are followed until first event or censoring. As a result, survival time will be calculated as: event or censoring date – reference date + 1. These are further described in Section 7.

When reporting survival or duration outcomes, the results (in days) above will be converted to an appropriate unit. When reporting in months it will be divided by 30.4375; for reporting in weeks it will be divided by 7; and for reporting in years it will be divided by 365.25.

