5.4. Study Time Periods

Safety reporting will be classified by the following study periods for analysis:

Pre-therapy is defined as the period prior to a subject's first dose of study treatment.

On therapy is defined as the period between first dose of study treatment and within 30 days following the last dose of study treatment.

Post-therapy is defined as the period of time following the on therapy period.

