For each visit-specific disease assessment, the date of overall response will need to be established. For complete response (CR) and partial response (PR), set the date of overall response to the latest of all tumor assessments for the specified visit. Otherwise, set to the earliest date of all assessments made during the specified visit.

Treatment End Date

Missing treatment end dates will not necessarily be imputed at the end of the study. However, due to ongoing reporting needs, treatment end date will be imputed as the earliest of the data cutoff date, date of death, or date of treatment study withdrawal.

End of Study Date

Missing study end dates will not necessarily be imputed at the end of the study. However, due to ongoing reporting needs, end of study dates will be imputed as the earliest of the data cutoff date or date of death.

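### The subject-year adjusted adverse event rate in SAP 8.1 counts each subject once but divides by time that neither stops at the first event nor matches the TEAE window, so for common events it falls with treatment length at equal hazard

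*SAP*

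**What the plan says.** SAP 8.1 states the purpose of the rate: "To account for potential differences in the extent of exposure between the treatment categories". It then gives the formula: "The rate is calculated as the number of subjects with an event divided by the total subject-years of safety observation". The time comes from SAP 5.3: "Duration of the safety observation period is defined as (the last date of treatment + 30 days"), minus the first dose date, plus 1.

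The numerator follows other rules, also in SAP 8.1. Within a preferred term, "subjects will be counted once within a PT based on their TEAE having maximum severity". A TEAE can arise from first dose "until 30 days following the last dose of study drug or initiation of subsequent cancer-related therapy, whichever occurs first".

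For subjects still on treatment, SAP 5.3 refers to the imputed dates in SAP 5.6, where "treatment end date will be imputed as the earliest of the data cutoff date, date of death, or date of treatment study withdrawal". The 30 days of SAP 5.3 are then added to that date.

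SAP 5.4 defines a third window, again without a cut at new therapy: "On therapy is defined as the period between first dose of study treatment and within 30 days following the last dose of study treatment".

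For Phase 1, SAP 8.1 counts infusion-related reactions (IRRs) only if, among other conditions, they "have an onset date on or one day after the date of a CRS-207 administration".

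**The concern.** A count of subjects with a first event gives an incidence rate only when it is divided by the time during which a first event could still occur. The SAP divides by all time up to last dose + 30 days. Two consequences follow.

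- **First-event effect.** After a subject's event, further time lowers the rate but cannot raise the count. The longer a group is treated, the more such time it has, so its rate falls at unchanged risk. This is the exposure dependence that the rate is meant to remove.
- **Window mismatch.** Days after new cancer therapy, after death, or beyond the data cut-off enter the denominator although no TEAE can be counted in them. This lowers rates.

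SAP 9 drops summaries of efficacy, so the safety tables are the main summarized output of the CSR synopsis. A rate shown there by arm should not depend on treatment length alone.

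**Working it through.** The documents give no numerical adverse event rate, so there is no figure to reproduce. They also give no treatment durations or hazards; those below are assumptions.

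**Step 1. Denominator per subject.** Let T = last minus first dose date in days. SAP 5.3 gives T + 31 days, so o = (T + 31)/365.25 years. For T = 63, o = 94/365.25 = 0.2574. For T = 189, o = 220/365.25 = 0.6023.

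**Step 2. Equal constant hazard L in both groups.** The probability of at least one event is 1 − exp(−L·o), so the SAP rate is (1 − exp(−L·o))/o. At L = 4:
- T = 63: (1 − exp(−1.029))/0.2574 = 0.643/0.2574 = 2.50
- T = 189: (1 − exp(−2.409))/0.6023 = 0.910/0.6023 = 1.51
- ratio 1.65, although the hazards are identical.

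| Hazard per subject-year | SAP rate, T = 63 | SAP rate, T = 189 | SAP rate ratio | Ratio of crude percentages |
|---|---|---|---|---|
| 0.1 | 0.099 | 0.097 | 1.02 | 0.44 |
| 0.5 | 0.469 | 0.432 | 1.09 | 0.46 |
| 1 | 0.882 | 0.751 | 1.17 | 0.50 |
| 2 | 1.563 | 1.162 | 1.35 | 0.58 |
| 4 | 2.498 | 1.511 | 1.65 | 0.71 |
| 8 | 3.390 | 1.647 | 2.06 | 0.88 |

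For infrequent events the SAP rate removes nearly all of the exposure difference that the crude percentage carries. Somewhere between hazards 2 and 4 it becomes further from 1 than the crude percentage.

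**Step 3. Size of the padding.** Protocol Table 1 places the end-of-treatment visit at least 7 days after the last CRS-207 dose and requires a 7-day antibiotic course before new therapy. New therapy then starts about day 14 after CRS-207, leaving 30 − 14 = 16 days that cannot count. If half of the subjects start then, the average is 8 days: 8/94 = 8.5% of the denominator at T = 63 and 8/220 = 3.6% at T = 189. The share is larger if another study drug was the last dose, and at most 30 days per subject are involved.

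**Step 4. Both effects together.** A simulation used 400,000 subjects per arm and exponential treatment durations with medians 3.6 and 5.6 months (the PFS medians in SAP 3.3, used as stand-ins). New therapy started at day 14 in 50%, and 5% died within 30 days.
- SAP rate ratio: 1.02, 1.08, 1.15, 1.24, 1.32 and 1.40 at hazards 0.1, 0.5, 1, 2, 4 and 8.
- Padding removed only, hazard 1: 1.147 becomes 1.166. The padding slightly offsets the first-event effect, because it lowers the shorter arm's rate more.
- Padding removed and time stopped at the first event: 0.998 to 1.006 for hazards 0.5 to 8, and 1.017 at 0.1. The last rests on about 0.048 × 400,000 = 19,200 and 0.069 × 400,000 = 27,600 events. The standard error of the log ratio is √(1/19,200 + 1/27,600) = 0.0094, so 1.017 is within two standard errors of 1.

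**Step 5. Events clustered at an infusion.** Suppose 80% in both groups have pyrexia at the first infusion and nobody later, with 93 or 186 days of observation.
- SAP formula: 0.8/(93/365.25) = 3.14 and 0.8/(186/365.25) = 1.57, ratio 2.00.
- Time stopped at the first event (1 day for reactors): 0.8 × 365.25/(0.8 + 0.2 × 93) = 292.2/19.4 = 15.06 and 292.2/(0.8 + 0.2 × 186) = 292.2/38.0 = 7.69, ratio 1.96.

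The stopping rule barely helps here, because the hazard is not constant. For Phase 1 IRRs only 2 days per infusion can count: 12 of 136 days (8.8%) with 6 infusions and 20 of 304 days (6.6%) with 10.

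**The case against.** The strongest defence is that the rate does most of what it is for and that little rides on it. For rare preferred terms and fatal events it comes within 2 to 9% of equality, where crude percentages differ about two-fold. It is shown beside counts and percentages, SAP 4 plans no significance test and SAP 3.3 no formal comparison between arms. Post-infusion fever, chills and nausea are already covered by the separate IRR summary in SAP 8.1. All of this stands. It limits the seriousness, but a descriptive figure that is offered as exposure-adjusted should still be so for common events.

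A reader might infer that the rate creates arm differences in place of removing them. The documents do not support that in general: it fails for infrequent events, and nothing in the documents shows that the arms' treatment durations differ.

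A reader might also infer that the padding drives arm differences. In the modelled case it moved the ratio by about 0.02, and towards 1. It would matter more if arms differed in how many subjects start new therapy or die within 30 days.

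Nor is it established that 30 unobserved days are added for each of the 2 subjects who may continue treatment: SAP 3.5 says data collection for them continues to soft-lock. For them the overrun is at most 2 × 30 = 60 subject-days. With data taken through 12 January 2018, anyone else last dosed after 13 December 2017 would also get days past that date; their number is not given.

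**Conclusion.** The point holds in a limited form. The SAP 8.1 rate is not an incidence rate, and its denominator does not match the TEAE window. For common events it falls with treatment length at equal hazard: ratios of about 1.17, 1.35 and 1.65 at hazards of 1, 2 and 4 per subject-year, for assumed durations of 63 and 189 days. A smaller gap in duration gives a smaller distortion (1.15, 1.24 and 1.32 in the simulation). For events up to about 0.5 per subject-year the effect is minor, and the padding is a small downward effect on rates. These sizes rest on assumed durations, constant hazards, and assumed shares starting new therapy or dying.

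It might be inferred that stopping time at the first event cures every case. It does not: for reactions clustered at CRS-207 infusions neither formula removes the dependence on duration. The correction should be made, but it concerns a supplementary descriptive statistic.

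**What to change.** In SAP 8.1, define the rate as subjects with the event divided by the sum of time at risk. Time at risk runs from first dose to the earliest of first such event, last dose + 30 days, start of subsequent cancer therapy, death and data cut-off, computed separately for each reported row.

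Do not carry the first-event stop into the SAP 5.4 on-therapy period or the general SAP 5.3 duration. The on-therapy period also governs extreme laboratory values (SAP 5.5), concomitant medication (SAP 6.6), worst ECG (SAP 8.3) and flags in the adverse event listing. A first-event stop there would damage those outputs.

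Do not present a subject-year rate for IRRs. Use the percentages and the IRR counts with number of infusions that SAP 8.1 already plans, expressed as IRRs per infusion.

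The cost is a separate denominator for each SOC/PT row, so one total per arm no longer serves the whole table. The event and new-therapy dates are already needed to classify TEAEs, so no new data are required.

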8.2. Clinical Laboratory Evaluations

Clinical chemistry and hematology parameters will be reported based on the International System of Units (SI). The following laboratory evaluations will be collected, those with asterisks (*) indicating those that will be graded using NCI-CTCAE v 4.03:

Hematology: hematocrit, hemoglobin*, red blood cell (RBC), platelet count*, white blood cell (WBC)*, absolute neutrophil count*, absolute lymphocyte count*, monocytes, eosinophils, and basophils.

Clinical chemistry: Electrolytes: bicarbonate, calcium*, chloride, magnesium*, phosphorus*, potassium*, sodium*; Hepatic function tests: albumin*, alkaline phosphatase*, bilirubin (total*, direct, indirect), total protein, alanine aminotransferase (ALT)*, aspartate aminotransferase (AST)*; renal function tests: blood urea nitrogen (BUN), creatinine*; Other chemistry tests: glucose*, LDH, amylase*, uric acid*. Note: Uric acid is graded only for Grade 4 as other grades require additional, clinical judgement. It will otherwise be assumed normal (Grade 0).

Coagulation: Activated partial thromboplastin time*, international normalized ratio, D-dimer, and fibrinogen*.

Endocrine testing (for subjects treated with epacadostat): Adrenocorticotropic hormone, serum cortisol, luteinizing hormone, prolactin, thyroid stimulating hormone, T3, FT3, FT4.

Thyroid function testing: Total triiodothyronine (T3), free triiodothyronine (FT3), free thyroxine (FT4), thyroid stimulating hormone.

Shift tables displaying the shift from baseline to the worst value of NCI-CTCAE grades for hematology and clinical chemistry parameters will be presented based on the most extreme change as it relates to the relevant NCI-CTCAE definition. NCI-CTCAE relating to “high/hyper” conditions will depend on the maximum post-baseline value while NCI-CTCAE “low/hypo” will be reported based on the minimum post-baseline value. Shift tables will also include parameters with bi-directional toxicity grading.

All laboratory parameters will be provided in subject data listings. Laboratory evaluations with a CTCAE grade of 3 or higher will also be provided as a separate listing.

8.3. Other Safety Evaluations

Vital Signs

Vital signs include: pulse (bpm); respiratory rate (breaths/min); temperature (°C); systolic and diastolic blood pressure (mmHg); pulse oximetry (%), and weight (kg).

Vital sign data will be provided in data listings.

Sponsor: Aduro Biotech, Inc.
Protocol Number: ADU-CL-11
Version and Date: Version 1.0, 03MAY2018

Electrocardiogram (ECG)

Electrocardiogram (ECG) parameters include HR (bpm) and the following intervals (ms): PR, QRS, QT, JTc, and QTcF. Observed values for ECG parameters will be listed.

Shifts in investigator-reported ECG interpretation shifts from screening worst case post-baseline will be summarized. Worst case post-baseline will be based on a subject's most abnormal observed investigator-reported ECG interpretation during the on therapy period.

ECG data will be provided in data listings.

ECOG Performance Status

ECOG data will be provided in data listings.

Physical Examinations

Physical examinations will be presented in subject data listings.

9. CHANGES TO THE PLANNED ANALYSIS

All efficacy endpoints will be derived and listed, but will not be summarized.

Sponsor: Aduro Biotech, Inc.
Protocol Number: ADU-CL-11
Version and Date: Version 1.0, 03MAY2018

